11.1 How will you measure, manipulate and/or analyse the information that you collect/gather?

The primary and secondary outcomes will be measured using validated scales. Primary outcome: Diabetes distress (measured using the Problem Area in Diabetes (PAID) scale); secondary outcomes: depressive and anxiety symptoms (measured using the Kessler Psychological Distress Scale (K10), emotional well-being (measured using the WHO-5), coping self-efficacy (measured using the Coping Self-Efficacy scale). Analyses will be conducted on an intention-to-treat (ITT) basis. Repeated measures analysis of variance (ANOVA), or a mixed model analysis (residual maximum likelihood (REML) method) will be used to analyse the primary and secondary outcomes.(52) The null hypothesis, that there is no interaction between assessment time (baseline and T6 months) and trial arm (Control vs Intervention), will be tested using an F-test conducted at the 5% significance level (α =0.05). In the event that some participants have missing assessments at T6 months, the analysis of variance will be replaced by a mixed model analysis using the REML method. A per protocol set (PPS) will be defined prior to any analyses and will be used for a sensitivity analysis of the primary endpoint.

Qualitative data from semi-structured interviews will be de-identified, transcribed verbatim and imported into NVivo. Thematic analyses will be used to explore and identify key themes about participant's experiences of the LISTEN intervention, preferences for modalities and suggestions for improvement as well as perceived barriers and facilitators to adoption and implementation reported by stakeholders from partner organisations.

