intervention or control (usual care), using a computer-generated program, to ensure allocation concealment. Randomisation (using stratified random permuted blocks) will be conducted in random blocks (4, 6 or 8), stratified by diabetes type, gender and age (<60; ≥60 years old). Researchers and data analyst will be blinded to group allocation.

The intervention group will receive LISTEN (1-4 weekly sessions; 45-60 minutes each), delivered via telehealth by a trained AHP.

Intervention: The core of LISTEN, problem-solving skills,³ provides participants with guidance and support to identify problems that may be contributing to their psychological distress; identify clear goals; brainstorm multiple solutions; weigh up pros and cons for each; choose a preferred solution; make a specific action plan to implement it; evaluate the outcomes from the previous session. Participants will work through up to four identified problems causing psychological distress. Participants will receive information and worksheets that will help support them between sessions and plan meaningful and enjoyable activities during the week. Strategies for working through problems that cannot be 'solved' will also be addressed. In addition, AHPs will encourage support-seeking behaviours. They will discuss how and when to seek support from mental health services, and how address their barriers for seeking support from a general practitioner or mental health professional.

[figure not shown]

Figure 1. The seven problem-solving skills in the LISTEN program⁴

Control: The control group will receive usual care including weblinks to NDSS factsheets about mental health (freely available on the NDSS website: https://www.ndss.com.au/living-with-diabetes/health-management/mental-health/), as well as links to external mental health support (e.g. Beyond blue) and if needed, a referral to their GP to discuss the best support for their emotional wellbeing. Recruitment will be primarily via the NDSS registrant database.

Outcomes: The primary outcome, diabetes distress, will be assessed at 6 months (primary endpoint) using the Problem Area in Diabetes (PAID) scale. Secondary outcomes will include: depressive and anxiety symptoms, assessed using the Kessler Psychological Distress Scale (K10),(46), emotional wellbeing (WHO-5),[48] and the Coping Self-Efficacy Scale (CSES).(47) The immediate effect (8

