7.2 The inclusion and exclusion criteria

To be eligible to participate, AHP participants must meet the following criteria:

- qualified allied health professional experienced in providing diabetes treatment and/or education to adults with diabetes (a minimum of 12 months working in a diabetes setting)
- previous training or experience in supporting people with emotional problems
- willingness and availability to undertake the training and deliver the LISTEN program

To be eligible to participate as a training case (Objective 2) or participate in the effectiveness trial (Objective 3) people with diabetes must meet the following criteria.

- living in Australia
- aged 18 years or older
- have a diagnosis of diabetes (with or without CVD)
- have a total score of 25 or greater on the Problem Areas In Diabetes (PAID) scale, indicating at least mild diabetes distress
- have a score less than 6 on the four-item Patient Health Questionnaire (50) (PHQ-4; a score greater than or equal to 6 indicates moderate-severe symptoms and warrants further assessment and follow-up)

The following pathways for people with diabetes will be applied depending on their scores:

Table 1: Eligibility criteria for the RCT (Objective 3) in terms of mental health screening

Participants' sco	re on:	Criteria	Eligible
PAID (0-100)	PHQ-4	Cineria	
Total <25	<6	No/minor diabetes distress and no/mild general symptoms	Noa
Total <25; and \geq 2 on \geq 3 items#	<6	Mild diabetes distress and no/mild general symptoms	Yes
Total 25-75	<6	Moderate-to-severe diabetes distress but no/mild general symptoms	Yes
Total >75	<6	Severe diabetes distress but no/mild depressive or anxiety symptoms	Yes
Total >75	>6	Severe diabetes distress plus at least moderate depressive or anxiety symptoms	Nob

[#] Score of ≥ 2 on a PAID item = at least moderate problem;

To be eligible to participate in the semi-structured interviews (Objective 5), stakeholders from the partner organisations must be an AHP who is a consenting participant in the project, or is a staff member employed at one of the partner organisations who is involved in the service delivery of the LISTEN intervention.

7.4 Your participant recruitment strategies and timeframes (as required in addition to that outlined in the HREA)

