11.4 Please include your statistical power calculation

We base our estimates upon Rees et al's (22) 6-month diabetes distress (measured with the Diabetes Distress Scale).(3) Assuming an alpha of 5%, we estimate requiring a total sample of N=226-302 participants (n=113-151 per arm), which will allow us to detect an effect size of 0.3 (Cohen's d) with power of 0.8-0.9. Allowing for a 50% attrition rate, we aim to recruit 454-604 participants. Based upon prior experience using the NDSS database for recruitment purposes, with a response rate of approximately 1.5%, we estimate to recruit a sample of N=454 participants, study invitations, and 2- week follow-up reminders, must be sent to a random sample of at least N=30,267 NDSS registrants. E-mail invitations will be staggered over the 6-month recruitment period (see **Section 7.4**).

The revised sample size calculation (amended from the study protocol V4 December 2022) is informed by a review of the completion rates for the incoming 8-week follow-up survey. We currently have a 71% response rate (i.e., ~30% attrition rate) across both the control and intervention groups (N=143/198). We have discussed this with the project statistician and the attrition rate for the 6-month survey is expected to be similar. As such, we anticipate the attrition rate across both time points to be 40-50%.

12. Data Linkage:

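### The primary test is an unadjusted time-by-arm interaction; adjusting 6-month PAID for the baseline PAID already collected would be more precise at no cost

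*Protocol*

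**What the plan says.** The primary endpoint is a single time point (protocol 6.1, Objective 3): "The primary outcome, diabetes distress, will be assessed at 6 months (primary endpoint) using the Problem Area in Diabetes (PAID) scale". The analysis in 11.1 is framed differently. "Repeated measures analysis of variance (ANOVA), or a mixed model analysis (residual maximum likelihood (REML) method) will be used", and the null hypothesis is "The null hypothesis, that there is no interaction between assessment time (baseline and T6 months) and trial arm (Control vs Intervention", which "will be tested using an F-test conducted at the 5% significance level". If 6-month assessments are missing, "the analysis of variance will be replaced by a mixed model analysis using the REML method"; 11.3 repeats that missing data are handled this way. No covariate is named.

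Randomisation is "stratified by diabetes type, gender and age" (6.1); 11.1 does not mention these factors. Entry requires participants to "have a total score of 25 or greater on the Problem Areas In Diabetes (PAID) scale" (7.2), although Table 1 also admits some people below 25. The schedule in 13.1 collects PAID at screening, 8 weeks and 6 months, so the screening score is the baseline value.

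On sample size, 11.4 says "we estimate requiring a total sample of N=226-302 participants (n=113-151 per arm"), for an effect size of 0.3 with power 0.8-0.9. It allows for 50% attrition and anticipates 40-50% over both time points. It states neither an analysis model nor a correlation.

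**The concern.** In a randomised trial the arms have the same expected baseline mean, so any observed baseline difference is chance. The interaction test subtracts the whole of that difference. Baseline adjustment subtracts only the part that carries through to 6 months, which is the better use of the same data unless the 6-month-on-baseline slope is 1.

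11.1 names the hypothesis, the test and the candidate models, so this is a stated method and not a detail left open. A statistical analysis plan that followed the text would carry over the less precise test. At stake is power in a trial that expects to lose up to half its participants, where buying the same precision by extra recruitment would be expensive.

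**Working it through.** **Inputs.** From 11.4: d = 0.3, 113 and 151 completers per arm, 50% attrition planned for and 40-50% anticipated. From 11.1: alpha 5%; the F-test is two-sided by nature. Assumed, because the protocol gives none: baseline to 6-month correlation r of 0.4-0.6 (0.7 and 0.8 also shown); d standardised by the 6-month SD; baseline SD equal to 6-month SD (relaxed below); dropout missing at random and equal between arms; only the two time points named in the null hypothesis are used.

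**The plan's own figure.** A two-sided two-sample t-test at d = 0.3 needs 176 per arm for 80% power and 235 for 90%. At 113 and 151 per arm its power is 0.61 and 0.74. So 113-151 does not follow from d = 0.3 and alpha 5% alone. It is reproduced by a baseline-adjusted analysis with r = 0.6 (variance factor 1 - 0.36 = 0.64). The attrition step is sound: 302/0.5 = 604 as stated, and 226/0.5 = 452 against the stated 454.

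**Variance factors**, in units of the 6-month variance, per completer:
- Baseline-adjusted: 1 - r².
- Interaction, complete data (change-score t-test): 2(1 - r).
- Interaction, REML with completer share f and everyone's baseline retained: (1 - r²) + f(1 - r)². At f = 1 this equals 2(1 - r).

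The REML form arises because the 6-month mean is estimated as the completers' mean, regression-corrected to the baseline mean of all participants (variance 1 - r² per completer). Subtracting that full baseline mean leaves a coefficient of r - 1 on it, and its variance is f times smaller per completer.

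**Numbers at f = 0.5:**
- r = 0.4: 0.84 + 0.5 × 0.36 = 1.02; ratio to adjusted 1.02/0.84 = 1.21
- r = 0.5: 0.75 + 0.5 × 0.25 = 0.875; ratio 0.875/0.75 = 1.17
- r = 0.6: 0.64 + 0.5 × 0.16 = 0.72; ratio 0.72/0.64 = 1.13

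At f = 0.6 (40% attrition) the ratios are 1.26, 1.20 and 1.15.

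**Power** (noncentral t, noncentrality 0.3 × √(n/2) / √factor, f = 0.5):

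| r | 113 per arm: REML interaction | 113: baseline-adjusted | 151 per arm: REML interaction | 151: baseline-adjusted |
|---|---|---|---|---|
| 0.4 | 0.604 | 0.688 | 0.730 | 0.809 |
| 0.5 | 0.670 | 0.737 | 0.793 | 0.851 |
| 0.6 | 0.754 | 0.801 | 0.865 | 0.901 |
| 0.7 | 0.854 | 0.882 | 0.937 | 0.953 |
| 0.8 | 0.954 | 0.963 | 0.988 | 0.991 |

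**Unequal SDs.** If the baseline SD is k times the 6-month SD, the extra term becomes f(k - r)². At k = 0.8 (assumption) and f = 0.5:
- r = 0.4: (0.84 + 0.08)/0.84 = 1.10
- r = 0.5: (0.75 + 0.045)/0.75 = 1.06
- r = 0.6: (0.64 + 0.02)/0.64 = 1.03; power at 113 per arm is 0.789 against 0.801.

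**The case against.** The strongest reply is that the test is unbiased and valid under randomisation, that the mixed model closes part of the gap, and that the remaining loss depends on an r and an SD ratio the protocol does not give. The entry threshold cuts both ways: selecting on PAID tends to lower r, which widens the gap, but it also narrows the baseline SD, which shrinks it. All of this stands. It limits the size of the point, not its direction: baseline adjustment is at least as precise at every r and k, apart from one degree of freedom.

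A reader might infer more, in four ways that the documents do not support.

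- That the full change-score penalty applies: ratios 2/(1 + r) of 1.43 to 1.25 for r = 0.4-0.6, or 20-30% of completers. That describes complete data. With the anticipated attrition, 11.1 switches to REML.
- That the test is worse than ignoring baseline whenever r is below 0.5. That too is a complete-data, equal-SD result. Under REML with half the participants completing, the crossover is at about r = 0.41, and nothing in the protocol shows that r is that low.
- That the strata are excluded and the type I error is therefore below 5% by a known amount. 11.1 is silent, and the covariate list may stand in a statistical analysis plan not shown here. No figure for the variance the strata explain is given.
- That the test contradicts the sample size. 113-151 fits baseline adjustment at r = 0.6, but the interaction test reaches about the same power at r of about 0.68 with complete data, or about 0.65 under REML with f = 0.5. As 11.4 states no model, no contradiction can be shown.

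**Conclusion.** The point holds as an efficiency recommendation. For r = 0.4-0.6, equal SDs and 50% attrition, the planned test has a variance 13-21% larger than a baseline-adjusted analysis. That is equivalent to losing 11% (1 - 1/1.125) to 18% (1 - 1/1.214) of completers, about 13 to 20 of 113 per arm. In power it is about 5 to 8 points at 113 per arm and 4 to 8 at 151. The difference is about 3 points or less at r = 0.7 and above, and about 1 point at r = 0.6 if the baseline SD is 0.8 of the 6-month SD. There is no bias and no inflated error rate. The case for adding the strata is good practice after stratified randomisation; its gain cannot be quantified from the protocol.

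**What to change.** In 11.1, replace the interaction hypothesis with the between-arm difference in 6-month PAID, estimated from a linear or mixed model adjusted for baseline PAID (or a mixed model with a common baseline mean in both arms), and include diabetes type, gender and age group (<60, ≥60). Use the same form for K10, WHO-5 and CSES, each with its own baseline. In 11.4, state the model and the correlation that give 113-151 per arm.

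The cost is wording only: every covariate is already collected. The change should be made before any outcome data are examined by arm, so that it cannot appear driven by the results.

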11.2 Please describe your matching and sampling strategies

The sampling strategy is outlined in section 7.4. Briefly, the primary method of recruitment will be a national e-mail using the NDSS registry. The NDSS will send out invitations directly to potential participants. The research team will not have access to potential participant's details unless they contact us regarding the study, or they enrol into the study (See 7.4 for more details on recruitment). Matching will not be undertaken as participants will be randomised once they have consented to being involved in the study (see 11.3).

11.3 Please outline how you will account for potential bias, confounding factors and missing information

Within the sample that respond positively to being involved in the study, potential bias will be accounted for by randomising to either the intervention or study arm. This will be done using a permuted block approach and will not be undertaken directly by the study team. In the event of missing information/data, this will be accounted for by using mixed model analysis described in section 11.1. Due to the nature of recruitment we will not be able to account for any biases that may exist between those who enrol in the study and those that did not respond to the email invitation.

11.4 Please include your statistical power calculation

We base our estimates upon Rees et al's (22) 6-month diabetes distress (measured with the Diabetes Distress Scale).(3) Assuming an alpha of 5%, we estimate requiring a total sample of N=226-302 participants (n=113-151 per arm), which will allow us to detect an effect size of 0.3 (Cohen's d) with power of 0.8-0.9. Allowing for a 50% attrition rate, we aim to recruit 454-604 participants. Based upon prior experience using the NDSS database for recruitment purposes, with a response rate of approximately 1.5%, we estimate to recruit a sample of N=454 participants, study invitations, and 2- week follow-up reminders, must be sent to a random sample of at least N=30,267 NDSS registrants. E-mail invitations will be staggered over the 6-month recruitment period (see **Section 7.4**).

The revised sample size calculation (amended from the study protocol V4 December 2022) is informed by a review of the completion rates for the incoming 8-week follow-up survey. We currently have a 71% response rate (i.e., ~30% attrition rate) across both the control and intervention groups (N=143/198). We have discussed this with the project statistician and the attrition rate for the 6-month survey is expected to be similar. As such, we anticipate the attrition rate across both time points to be 40-50%.

12. Data Linkage:

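### Section 11.4 claims 80-90% power for d = 0.3 with 113-151 per arm, but its stated inputs give about 61% and 74%; the claim depends on an undeclared baseline-to-6-month correlation.

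*Protocol*

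**What the plan says.** Section 11.4 of the protocol sets alpha at 5% and states "we estimate requiring a total sample of N=226-302 participants (n=113-151 per arm), which will allow us to detect an effect size of 0.3". The effect is expressed as Cohen's d, and the two sample sizes are tied to 80% and 90% power respectively. The section then allows for 50% attrition, which gives the recruitment target of 454-604. The effect is taken from an earlier trial's "6-month diabetes distress (measured with the Diabetes Distress Scale"). The section names no test, no sidedness, no standard deviation and no correlation between baseline and follow-up.

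Section 11.1 describes the primary analysis as a repeated measures ANOVA or, if 6-month assessments are missing, a REML mixed model. The null hypothesis is "no interaction between assessment time (baseline and T6 months) and trial arm (Control vs Intervention"), and it "will be tested using an F-test conducted at the 5% significance level". ANCOVA is not mentioned, and section 11.1 gives no correlation either.

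**The concern.** A reader who enters the stated inputs into any standard two-sample calculation gets a sample size about half as large again as the protocol's. Some input that reduces the variance has been used but not declared, and the result depends on it.

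The figure of 226-302 completers is the base for the 454-604 target, which appears in sections 6.1, 7.1, 7.4, 9.1 and 11.4. The current amendment revisits attrition but leaves the completer number beneath it unexplained. If the true correlation is lower than the one assumed, the trial will have less power at its planned number of completers than it reports.

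**Working it through.** **Inputs.** d = 0.3, alpha 5%, power 0.80 and 0.90, and 113 and 151 per arm are all from section 11.4. Two-sided testing is inferred from section 11.1, because an F-test with one numerator degree of freedom is equivalent to a two-sided t-test. The correlation r between baseline and 6-month PAID is not given, so it is varied.

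**Step 1: the stated inputs alone.** With SD = 1, the approximate number per arm is

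n = 2 × (z₀.₉₇₅ + z_power)² / d².

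- 80% power: 2 × (1.960 + 0.842)² / 0.09 ≈ 175; the exact noncentral-t calculation gives 175.4, so 176.
- 90% power: 2 × (1.960 + 1.282)² / 0.09 ≈ 234; the exact calculation gives 234.5, so 235.

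Turned round, exact power is 0.612 with 113 per arm and 0.738 with 151. The normal approximation gives 0.616 and 0.741. The shortfall against 0.80 and 0.90 is about 19 and 16 percentage points.

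**Step 2: one-sided testing.** At one-sided 5% the requirement is 139 and 191 per arm, and power at 113 and 151 is 0.727 and 0.830. This does not reproduce the stated figures either.

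**Step 3: what would reproduce 113 and 151.** The ratios 113/176 and 151/235 are both 0.64, so both figures imply the same variance factor: a reduction of about 36%. Two standard factors can supply it, with equal variances at the two times assumed for the second:

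- Baseline-adjusted analysis (ANCOVA, or a mixed model with a common baseline mean): factor 1 − r². Setting 1 − r² = 0.64 gives r = 0.60.
- Time-by-arm interaction over two time points, which is a comparison of change scores: factor 2(1 − r). Setting 2(1 − r) = 0.64 gives r = 0.68.

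Either way the exact calculation gives 112.6 and 150.4 per arm, which round up to the protocol's 113 and 151.

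**Step 4: power at 113 / 151 per arm over a range of r** (exact, two-sided 5%, d = 0.3).

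| r | Planned time-by-arm test | Baseline-adjusted |
|---|---|---|
| 0.5 | 61% / 74% | 74% / 85% |
| 0.6 | 71% / 83% | 80% / 90% |
| 0.68 | 80% / 90% | 87% / 94% |

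At r = 0.5 the factor 2(1 − r) equals 1, so the planned test gains nothing over ignoring baseline. At r = 0.6 it would need 141 and 188 per arm.

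**Step 5: attrition.** 226 / 0.5 = 452 (stated as 454) and 302 / 0.5 = 604, so this step is sound. Applied to 352 and 470 completers (2 × 176 and 2 × 235), the same 50% would give 704 and 940 recruited.

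**The case against.** A reader might infer that the calculation was done for an ANCOVA with r = 0.6 and that the plan then uses a different test, so that design and analysis do not match. The documents do not support this. The planned time-by-arm test with r = 0.68 gives the same two numbers, and the REML mixed model that section 11.1 allows could, with a common baseline mean, be about as efficient as ANCOVA. What is shown is a missing input, not a mismatch.

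A reader might also infer that the trial lacks the power it claims. That goes too far: with r of about 0.68 or more, the planned test has it.

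It is also tempting to argue that selecting participants on PAID must lower r and so worsen the shortfall. That cannot be quantified here. Selection on baseline also shrinks the baseline variance, which breaks the equal-variance assumption behind 2(1 − r). The protocol gives no PAID mean or SD, and its eligibility table admits some people with totals below 25.

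Finally, the low figures apply to 226-302 completers, that is to 50% attrition. Section 11.4 reports about 30% loss at 8 weeks, expects the 6-month loss to be similar, and anticipates 40-50% across both time points. If 454-604 were recruited and 40% lost, unadjusted power would be about 69% / 81%, and the planned test at r = 0.6 would have about 79% / 89%. With 30% lost, the figures are about 76% / 87% and 84% / 93%. This stands as a limit on the practical size of the problem. It does not rescue the statement in section 11.4, which ties 80-90% power to 113-151 completers per arm.

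**Conclusion.** The stated power does not follow from the stated inputs. With d = 0.3, two-sided 5% and 113 / 151 completers per arm, power is about 61% / 74%, not 80% / 90%. The claim holds only with an undeclared variance reduction of about 36%: r of at least about 0.68 under the planned time-by-arm test, or at least about 0.6 under a baseline-adjusted analysis.

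The result assumes 1:1 allocation and a d scaled by the SD of the 6-month score. The change-score figures also assume equal variances at baseline and 6 months. The true correlation is unknown from the documents, so the conclusion is that the claim is unsupported as written, not that the trial is shown to be underpowered.

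**What to change.** Restate section 11.4 along these lines: *226-302 completers give about 61-74% power for d = 0.3 (two-sided 5%) with no correlation assumed, and 80-90% only if the baseline-to-6-month correlation is at least about 0.68 under the planned time-by-arm test, or about 0.6 under a baseline-adjusted analysis.* Name the test and its sidedness, give the assumed correlation with its source, and show power over a range of correlations such as 0.5 to 0.7.

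As a further improvement, make the primary analysis in section 11.1 baseline-adjusted. The interaction test is valid, so this corrects no error. But 1 − r² = (1 − r)(1 + r) never exceeds 2(1 − r), so under the same assumptions adjustment is at least as efficient at any correlation.

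The cost is protocol wording and possibly a less favourable power statement. No additional participants are needed.
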